#### 5.1.2.1 Phase I:

**Table 1: Dose Escalation Schedule of Duvelisib and Venetoclax**

Dose Escalation Schedule		
Dose Level	Dose*	
	Duvelisib	Venetoclax
Level -1	25 mg BID	50 mg daily
Level +1(Starting Dose)	25 mg BID	100 mg daily
Level +2	25 mg BID	200 mg daily
Level +3	25 mg BID	400 mg daily

In the Phase I portion of the trial, we aim to determine the maximum tolerated dose (MTD) of venetoclax when given in combination with duvelisib. A standard 3+3 dose escalation design will be employed (Figure 4). Patients will be treated in cohorts of size three to six and the dosage will be escalated if the clinical toxicity is acceptable.

[figure not shown]

CONFIDENTIAL

This document is confidential. Do not disclose or use except as authorized.

**Figure 4: 3+3 dose escalation for the phase I trial:**

Dose escalation will proceed according to the following scheme:

The MTD is defined as the highest dose studied for which the observed incidence of DLT is less than 33%. Frequencies of toxicities will be tabulated according to the NCI Common Toxicity.

Once the MTD of venetoclax in combination with duvelisib is determined, patients assigned to lower dose levels of venetoclax will have the option of escalating their venetoclax dose to the MTD.

**5.1.2.2 Phase II:**

Patients in the phase II portion of the trial will also begin duvelisib on day 1 and add venetoclax on day 8. Please refer to section 5.1.2 for full venetoclax dose ramp up instructions. Patients will continue combination therapy for up to 12 cycles followed by venetoclax monotherapy until unacceptable toxicity, patient withdrawal, disease progression without clinical benefit, physician decision, physician/patient discussion of treatment discontinuation based on objective disease response, or death. Those patients who achieve CR/CRi with undetectable MRD in the bone marrow after 1 year of combination therapy have the option to discontinue study therapy and be monitored with the option to resume venetoclax monotherapy if at least 2 peripheral blood MRD tests come back as detectable. If they do not achieve MRD negativity or have evidence of disease progression after reaching full dose venetoclax monotherapy, they have the option to add duvelisib at the highest dose they previously tolerated and continue it until MRD negativity is achieved on two successive peripheral blood MRD assessments or indefinitely depending on tolerability.

Patients in the RS cohort will be treated similarly to those in the phase II CLL/SLL cohort with one week of duvelisib monotherapy prior to adding venetoclax. RS patients will also start with 20 mg of venetoclax with weekly ramp-up to 400 mg similar to the CLL/SLL cohort. However, given the potential for rapidly progressive RS, these RS patients will also have the option to undergo an accelerated venetoclax ramp-up modeled after another study of venetoclax plus chemotherapy that was recently reported ([name] et al., ICML, 2019). In that study, venetoclax was safely ramped up in a daily fashion for RS patients, who were monitored closely in the

CONFIDENTIAL

This document is confidential. Do not disclose or use except as authorized.

inpatient setting. The venetoclax is dosed at 20 mg for day 1, and if no TLS is observed on labs done 6-8 hours and 24 hours later, then the dose is ramped up to 50 mg on day 2, 100 mg on day 3, 200 mg on day 4, and 400 mg on day 5 if the daily labs done 6-8 hours and 24 hours later continue to show no TLS. If laboratory TLS does occur, the next day's dose will be held until there is improvement in the TLS, at which point escalation to the next dose may occur. If a treating investigator wishes to do this accelerated ramp-up, written approval must be obtained from the Overall PI (or delegate) prior to initiating venetoclax therapy.

## 5.2 Pre-Treatment Criteria

### 5.2.1 Cycle 1, Day 1:

Participants must meet all the inclusion criteria, have none of the exclusion criteria prior to treatment with the exception that patient's laboratory evaluations on C1D1 do not need to meet eligibility criteria again provided that they did meet criteria at screening and any changes in the patient's condition or labs do not in the opinion of the investigator pose significant risk to the patient. Participants must be registered to the protocol prior to initiating therapy.

### 5.2.2 Ramp-up cycles Day 1 of combination duvelisib and venetoclax therapy:

- ANC must be  $\geq 500/\text{mm}^3$  (growth factor support allowed), unless they have significant bone marrow involvement of CLL confirmed on pretreatment biopsy
- Platelet count must be  $\geq 20\text{K}$  (transfusion support allowed), unless they have significant bone marrow involvement of CLL confirmed on pretreatment biopsy
- Serum creatinine must be  $\leq 1.5$  times the upper limit of normal or creatinine clearance must be  $\geq 50 \text{ mL/min}$  using a 24-hour urine collection
- All non-hematologic toxicities must have resolved to  $\leq$  Grade 2, or to the patient's baseline condition
- No evidence of active tumor lysis syndrome

### 5.2.3 Combination cycles of duvelisib and venetoclax therapy and venetoclax monotherapy (maintenance) cycles

The following treatment parameters must be met at visits when a new cycle is being started:

- ANC must be  $\geq 500/\text{mm}^3$ , unless they have significant bone marrow involvement of CLL confirmed on pretreatment biopsy (growth factor support allowed)
- Platelet count must be  $\geq 20\text{K}$ , unless they have significant bone marrow involvement of CLL confirmed on pretreatment biopsy (transfusion support allowed)

CONFIDENTIAL

This document is confidential. Do not disclose or use except as authorized.

- All non-hematologic toxicities must have resolved to  $\leq$  Grade 2, or to the patient's baseline condition

### 5.3 Definition of Dose-Limiting Toxicity (DLT)

Dose-limiting toxicity (DLT) is based on the CTEP Active Version of the NCI Common Terminology Criteria for Adverse Events (CTCAE) Version 5.0. DLT refers to toxicities experienced at any time during the first cycle of study treatment, defined as the following:

- Grade 4 neutropenia lasting more than 5 days
- Febrile neutropenia of any duration ( $ANC < 1.0 \times 10^9/L$  and fever  $\geq 38.5^\circ F$ )
- Grade  $\geq 3$  thrombocytopenia with clinically significant bleeding
- Grade  $\geq 4$  infection by NCI-CTCAE criteria
- Any grade 3 or greater non-hematologic toxicity with the following exceptions:
  - Grade 3 or greater nausea/vomiting/diarrhea that persists for 7 days or less
  - Grade 3 asymptomatic laboratory abnormalities that improve to grade 2 or less within 3 days
- Any grade  $\geq 3$  diarrhea or vomiting or diarrhea that requires tube feeding, total parenteral nutrition, or requires or prolongs hospitalization
- Inability to receive Day 1 therapy of Cycle 2 after a delay in treatment of up to 21 days due to continued drug related toxicity from the prior cycle
- Severe cutaneous reaction (grade 3 or greater)
- Grade 4 elevation in ALT and/or AST or grade  $\geq 3$  elevation in ALT and/or AST occurring in the context of a Grade  $\geq 2$  elevation in bilirubin
- Grade 5 treatment-related adverse events

All toxicities will be considered relevant to determining DLTs and to reporting unless the event can clearly be determined to be unrelated to the study drug(s).

The DLT observation period is considered the period from the first dose of combination therapy through the completion of cycle 1. In the phase I study, if a patient comes off study due to a reason other than a DLT (e.g. disease progression) prior to the end of the DLT observation period, that patient can be replaced.

CONFIDENTIAL

This document is confidential. Do not disclose or use except as authorized.

Management and dose modifications associated with the above adverse events are outlined in Section 6.

### 5.3.1 Safety Rules and Data Safety and Monitoring Trigger for Enrollment Pause

The DF/HCC Data and Safety Monitoring Committee (DSMC) will review and monitor toxicity and accrual data from this study. The committee is composed of medical oncologists, research nurses, pharmacists and biostatisticians with direct experience in cancer clinical research. Information that raises any questions about participant safety will be addressed with the Overall PI and study team. This information can also be found in Appendix E addressed in more detail.

The DSMC will review each protocol up to four times a year with the frequency determined by the outcome of previous reviews. Information to be provided to the committee may include: up-to-date participant accrual; all grade 2 or higher unexpected adverse events that have been reported; summary of all deaths occurring within 30 days of intervention; any response information; audit results, and a summary provided by the study team. Other information (e.g. scans, laboratory values) will be provided upon request

## 5.4 General Concomitant Medication and Supportive Care Guidelines

Subjects should receive full supportive care, including transfusions of blood and blood products, antibiotics, hematopoietic growth factors, analgesics, and anti-emetics when appropriate. Local institutional standard of care may also be followed.

### 5.4.1 Tumor Lysis Syndrome (TLS) Prophylaxis:

Tumor lysis syndrome (TLS), characterized by hyperkalemia, hyperuricemia, and hyperphosphatemia resulting from the rapid release of potassium, uric acid, and phosphate, has been reported in patients receiving venetoclax, necessitating TLS prophylaxis. The risk of TLS is highest during initiation of venetoclax.

- All patients should be started on an oral uric acid reducer (such as allopurinol 300 mg/day) prior to initial study therapy administration (ideally at least 72 hours prior when possible) and continued until each subject has completed a week at their highest dose level of venetoclax, unless known allergy.
- Patients should remain well hydrated

The following is recommended for prophylaxis in patients being admitted for TLS observation.

- Administration of an oral uric acid reducer (such as allopurinol 300 mg/day) prior to initial study therapy administration (ideally at least 72 hours prior when possible) and continued until each subject has completed a week at their highest dose level of

CONFIDENTIAL

This document is confidential. Do not disclose or use except as authorized.

venetoclax. Patients with an allergy to allopurinol and thought to be at high risk for TLS, should receive a prophylactic dose of rasburicase prior to administration of venetoclax.

- IV hydration should be started the night before the first dose of 10 mg (during Phase II, before 10mg or 20mg as indicated), with a target of approximately 1.5 – 2 L/day, or as clinically appropriate, and continued for at least 24 hours after administration of venetoclax.
- Nephrology (or other acute dialysis service) consultation should be considered prior to dosing per institutional standards at the investigators' discretion to ensure emergency dialysis is available and the appropriate staff is aware and prepared to handle any necessary intervention for TLS.
- Telemetry should also be considered.
- Rasburicase (given at a flat dose of 6 mg IV x 1) must be administered per institutional guidelines for subjects with elevated uric acid level at baseline (> ULN) as prophylaxis prior to the initial dose of venetoclax. For subjects with a contraindication to rasburicase (i.e., glucose-6-phosphate dehydrogenase [G6PD] deficiency), the TLS risk mitigation plan must be reviewed with the Overall PI.
- Chemistry laboratory tests must be performed STAT at least at the following time points: pre-dose (within 4 hours before venetoclax administration), and approximately 4, 8, 12, and 24 hours after the first dose of venetoclax at 10 mg and each subsequent dose escalation. Pre-dose laboratory values will be collected and used as baseline to assess potential electrolyte abnormalities occurring post venetoclax administration.
- If any laboratory changes in potassium, uric acid, phosphate, calcium, lactate dehydrogenase, or creatinine are observed within the first 24 hours after initiation of dosing, see Appendix C (Recommendations for Initial Management of Electrolyte Abnormalities and Prevention of Tumor Lysis Syndrome [TLS]) for additional laboratory assessments and management guidelines.
- Patients without evidence of TLS can be discharged 24 hours following venetoclax administration

#### 5.4.2 Treatment of TLS:

All subjects meeting criteria of laboratory TLS or  $\geq$  grade 1 TLS according to the Cairo-Bishop Definition of Tumor Lysis Syndrome (see Appendix B) should receive vigorous intravenous hydration, aggressive electrolyte management, and should be considered for rasburicase therapy as needed to reduce hyperuricemia, until correction of electrolyte abnormalities. See Section 6, Dose Modification, for additional instructions.

#### 5.4.3 Monitoring for skin reactions:

Patients will be closely monitored for the development of a skin rash while being treated with duvelisib. Patients will also be informed to call their provider with any evidence of rash.

CONFIDENTIAL

This document is confidential. Do not disclose or use except as authorized.

#### 5.4.4 Prophylactic Antibiotics:

Prophylaxis for *Pneumocystis jiroveci* pneumonia (PCP) with Bactrim or equivalent, and anti-herpetic viral prophylaxis with acyclovir or equivalent is mandated beginning with cycle one and continuing for the duration of the participant's treatment on study.

#### 5.4.5 CMV Monitoring:

Based on data from the duvelisib phase I study in CLL, subjects taking duvelisib might be at an increased risk of cytomegalovirus (CMV) reactivation. Clinically significant CMV infection can generally be avoided by close monitoring and institution of anti-CMV therapy at time of positive viral load detection. Therefore, all subjects on study will have mandatory CMV viral measurement at study entry and monthly thereafter while on duvelisib therapy. Subjects whose CMV viral load becomes positive will be started on treatment dose valganciclovir and the CMV viral load will be checked weekly until it becomes undetectable. At that point, dosing of valganciclovir can be changed to the prophylactic dose for the remainder of the study. The subject should continue to undergo weekly CMV viral load surveillance for four consecutive negative tests and can then return to monthly testing thereafter. Alternative anti-herpetic viral prophylaxis should be stopped during valganciclovir dosing. Testing at outside laboratories will be allowed during months that the patient is not scheduled for clinic visits.

#### 5.4.6 Medications of Food that Inhibit or Induce CYP3A4/5:

In vitro data also indicate that oxidative metabolism may play an important role in the elimination of duvelisib and venetoclax, with CYP3A4/5 identified as the primary enzymes for metabolism. As duvelisib and venetoclax are moderate inhibitors of CYP3A4/5, there is potential for drug-drug interactions and increased exposures. Preliminary data from a drug-drug interaction study with ketoconazole (a potent CYP3A4/5 inhibitor) indicate exposure to duvelisib increased approximately 4- fold in the presence of ketoconazole. For this reason, the concomitant use of drugs or foods that are strong or moderate inhibitors or inducers of CYP3A are not allowed for 7 days prior to the first dose of duvelisib. Additionally, the use of these drugs and foods are not allowed during study treatment. Appendix D provides a list of medications known to be strong or moderate inhibitors or inducers of CYP3A. Please note that Appendix D is not a comprehensive list of all medications which may modulate CYP3A4/5 activity. The Principal Investigator should be contacted with any questions regarding concomitant use of medications that are thought to modulate CYP3A activity. The concomitant use of weak inhibitors may be allowed in selected circumstances after consultation with the Principal Investigator.

### 5.5 Criteria for Taking a Participant Off Protocol Therapy

CONFIDENTIAL

This document is confidential. Do not disclose or use except as authorized.

Duration of therapy will depend on individual response, evidence of disease progression and tolerance. In the absence of treatment delays due to adverse event(s), treatment may continue until one of the following criteria applies:

- Disease progression without clinical benefit
- Intercurrent illness that prevents further administration of treatment
- Unacceptable adverse event(s)
- Physician discretion
- After at least one year of treatment, if a patient achieves a complete remission (CR) or complete remission with incomplete count recovery (CRi) with MRD-negativity in the bone marrow, they will have the option to discontinue therapy and transition to active disease monitoring with the option to restart venetoclax if they experience disease recurrence as evidenced by at least two instances of MRD-detectability or clinical disease progression. If patients do not achieve MRD negativity or have evidence of disease progression after reaching full dose venetoclax monotherapy, they have the option to add duvelisib at the highest dose they previously tolerated and continue it until MRD negativity is achieved on two successive peripheral blood MRD assessments or indefinitely depending on tolerability
- If after 24 months of treatment (Cycle 25 restage) a patient achieves a PR with MRD negativity in the bone marrow, they will have the option to discontinue therapy and transition to active disease monitoring with the option to restart venetoclax if they experience disease recurrence as evidenced by at least two instances of MRD-detectability or clinical disease progression in the opinion of the investigator. If patients do not achieve MRD negativity or have evidence of disease progression after reaching full dose venetoclax monotherapy, they have the option to add duvelisib at the highest dose they previously tolerated and continue it until MRD negativity is achieved on two successive peripheral blood MRD assessments or indefinitely depending on tolerability
- Participant demonstrates an inability or unwillingness to comply with the oral medication regimen and/or documentation requirements
- Participant decides to withdraw from the protocol therapy
- General or specific changes in the participant's condition render the participant unacceptable for further treatment in the judgment of the treating investigator

Participants will be removed from the protocol therapy (treatment) when any of these criteria apply. The reason for removal from protocol therapy, and the date the participant was removed,

CONFIDENTIAL

This document is confidential. Do not disclose or use except as authorized.

must be documented in the case report form (CRF). Alternative care options will be discussed with the participant.

When a participant is removed from protocol therapy, they will remain on study in active follow up for up to one year or until withdrawal of consent, initiation of other CLL or Richter's directed therapy, or death. They will then be followed for survival indefinitely.

When a participant is off of the study completely (no longer in follow up or being followed for survival), the relevant Off-Treatment/Off-Study information will be relayed to the lead site study team, and updated in OnCore.

In the event of unusual or life-threatening complications, treating investigators must immediately notify the Overall PI, *[name]* at [contact], [name].

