## 5.6 Duration of Follow Up and Active Disease Monitoring

### Disease Monitoring:

Participants who elect to discontinue treatment after having achieved MRD negative CR or CRi (or MRD- PR after C25) will be followed every 3 months (+/- 14 days) for active disease monitoring. Subjects are allowed to alternate visits with a local team so that they only need to be seen at the trial site every 6 months. They will be monitored until they resume treatment with venetoclax (if they show signs of progression by MRD positivity or clinical manifestations) or are removed from active disease monitoring for other reasons such as withdrawal of consent, removal from monitoring by treating investigator, lost to follow up, elect to go on to other CLL/RS directed therapy, or death.

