### Follow Up:

Those who are removed from treatment for reasons other than MRD negativity will be followed every 3 months for up to one year (+/- 14 days). During active follow up (not those who are in active disease monitoring) participants will be offered the opportunity to have follow up visits at their treating institution every 6 months (versus every 3) to minimize travel burden if they choose, so long as they are being clinically followed by a hematologist/oncology team locally every other visit, and relevant clinical information is being conveyed to the lead site for follow up data entry purposes.

CONFIDENTIAL

This document is confidential. Do not disclose or use except as authorized.

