**Assessments for those who discontinue treatment for reasons other than MRD negative CR/Cri or PR after C25 :**

- History and physical
- CBC differential and platelet count
- Serum Chemistry Panel including magnesium, uric acid, phosphorus and LDH
- CT or PET CT scan and response assessment as clinically indicated
- Bone marrow biopsy and aspirate as clinically indicated

After the active disease monitoring and follow up periods are complete, survival follow up data will be collected indefinitely unless one of the following occurs:

- Death
- Lost to survival follow up
- Withdrawal of consent

Survival status may be collected by phone, email, or other traditional data collection methods indefinitely.

The reason for taking a participant off study, and the date the participant was removed, must be documented in the case report form (CRF).

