### 11.3.3 **Progression free Survival**

**Progression-Free Survival:** Progression-Free Survival (PFS) is defined as the time from registration to the earlier of progression or death due to any cause. Participants alive without disease progression are censored at date of last disease evaluation.

**Overall Survival:** Overall Survival (OS) is defined as the time registration to death due to any cause, or censored at date last known alive.

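### Disease follow-up ends within a year for patients who stop treatment for reasons other than MRD negativity, so PFS and DOR beyond about 12 months may be biased by treatment-dependent censoring

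*Combined protocol and SAP*

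**What the plan says.** Section 5.5 says of patients removed from protocol therapy that "they will remain on study in active follow up for up to one year", ending sooner on withdrawal of consent, a new CLL or Richter's therapy, or death. After that, "They will then be followed for survival indefinitely".

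Section 5.6 separates two groups. For ordinary stoppers: "Those who are removed from treatment for reasons other than MRD negativity will be followed every 3 months for up to one year". In that year imaging is not scheduled: "CT or PET CT scan and response assessment as clinically indicated". Afterwards, "survival follow up data will be collected indefinitely unless one of the following occurs" (death, loss to follow-up or withdrawal). For patients who stop because of MRD negativity there is no time limit: "They will be monitored until they resume treatment with venetoclax" or leave monitoring for another reason. Patients on treatment have visits every 3 cycles through cycle 60 and every 6 cycles after that (section 5, Phase II).

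Two censoring rules are given. Section 11.3.3 counts progression or death from any cause as a PFS event, and "Participants alive without disease progression are censored at date of last disease evaluation". Section 13.3 ends PFS at progression, death or last follow-up. It runs DOR from response to progression and censors patients still responding at last follow-up. Both endpoints use Kaplan-Meier. No sensitivity analysis is planned for this censoring.

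**The concern.** Kaplan-Meier estimates are valid when censored patients have the same future risk as those who remain under observation. Here the end of disease assessment is set by treatment status, and treatment status is plausibly related to risk: section 5.5 lists unacceptable adverse events, intercurrent illness, non-compliance and deterioration among the reasons for removal. Past the one-year limit, the curve rests on patients still on treatment or in MRD-negative monitoring.

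Deaths add a second problem. They are collected indefinitely and are PFS events under both sections. An ordinary stopper who dies late is therefore an event at the date of death, while the same patient, if alive, is censored back at the last disease evaluation. Time at risk then depends on the later outcome.

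The background sections justify the combination by the poor durability of single-agent responses, so the later part of these curves will be read closely.

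**Working it through.** The plan gives no assumed median, event count or power for PFS or DOR, so there is no stated figure to reproduce. Every rate below is an assumption.

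**Closed-form example (11.3.3 rule, late deaths left out).** A fraction f = 0.25 stops at month 6 and is censored 12 months later, at month 18. The progression hazard is h1 = 0.015 per month on treatment and h2 = 0.04 off treatment.

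- True S(t) = (1−f)·e^(−h1·t) + f·e^(−6·h1 − h2·(t−6)).
- After month 18 only on-treatment patients remain at risk, so the Kaplan-Meier limit is S(18)·e^(−h1·(t−18)).
- True S(36) = 0.75·e^(−0.54) + 0.25·e^(−1.29) = 0.4371 + 0.0688 = 50.6%.
- S(18) = 0.75·e^(−0.27) + 0.25·e^(−0.57) = 0.5725 + 0.1414 = 0.7139. Estimate at 36 months = 0.7139 × 0.7634 = 54.5%, which is 3.9 points too high.
- At 48 months the figures are 40.8% true and 45.5% estimated.

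**Same formula with other off-treatment hazards, at 36 months.**

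- h2 = 0.015 (ratio 1): both are 58.3%, so there is no bias.
- h2 = 0.0075 (ratio 0.5): true = 0.4371 + 0.25·e^(−0.315) = 0.6195; estimate = (0.5725 + 0.25·e^(−0.18)) × 0.7634 = 0.5965. The estimate is 2.3 points too low.

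**Wider range by simulation** (400,000 patients, exponential times). On-treatment median PFS is 13.3 or 22 months, borrowed from sections 2.4 and 2.3. Assumed: 20% or 40% stop without progression by month 12; 0% or 30% of stoppers start new therapy within 12 months (first three rows); data cut at 60 months. The last row assumes a mean of 6 or 24 months from progression to death. Entries are estimated minus true PFS, in percentage points.

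| Rule | Off/on hazard ratio | 24 months | 36 months |
|---|---|---|---|
| 11.3.3: censored when active follow-up ends | 1.5 to 3 | +0.5 to +3.0 | +0.8 to +4.2 |
| Same | 1 | 0 | 0 |
| Same | 0.5 | −0.9 to −2.5 | −2.6 to −4.7 |
| 13.3: event-free until death or data cut | 0.5 to 2 | +0.7 to +4.5 | +1.2 to +8.8 |

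In the last row the sign does not depend on risk: an unseen progression is replaced by a later death or by censoring at the data cut, so the curve can only move up.

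Under 11.3.3 with ratios of 1.5 to 3, the median moves by 0 to 0.5 months. The cap cannot act before month 12; censoring at new therapy adds at most about 0.7 points to 12-month PFS.

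**Late deaths counted as PFS events under 11.3.3** (mean progression-to-death lag 6 to 48 months, assumed). In the closed-form example the 36-month overstatement falls from 3.9 to about 1 to 3.5 points, and at 48 months to about 0 to 3. At ratio 1, PFS becomes understated by about 0 to 1.6 points at 36 months. The offset is not guaranteed, because patients who die late also stay longer in the risk set. In the simulated case with a 22-month median, 40% stopping and ratio 2 (no new therapy), the 36-month overstatement of 2.8 points becomes 2.2 with a 6-month lag and 5.1 with a 24-month lag. DOR gets no such offset, since 13.3 names only progression as its end.

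**Scale.** The standard error of a 24-month PFS of 42% with 35 patients is √(0.42 × 0.58/35) = 8.3 points.

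**The case against.** The strongest reply is that neither direction nor size is shown.

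- No section gives a progression risk after stopping, and upward bias under 11.3.3 appears only if a ratio above 1 is assumed.
- Good-prognosis patients also leave: responders may go to transplant, and treatment may end by agreement on the basis of objective response.
- The cap applies only after removal from all protocol therapy. A patient who stops one drug can continue the other, so toxicity often leaves the patient on the treatment schedule. A 25% stopping rate has no source in the documents.
- The contrast in assessment is less sharp than it looks. On-treatment scans after cycle 13 are partly discretionary, and scans for MRD-negative stoppers are only as clinically indicated.
- PFS and DOR are secondary, with no hypothesis or decision rule, and the possible bias is smaller than the sampling error.

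All of this stands against a firm claim about direction or size. It does not remove the problem. Visits, which are how progression comes to be suspected and scanned, stop for one group and not for the others. The mix of good and poor exits makes the sign uncertain without making the censoring neutral. Sampling error shows in the confidence interval; this bias does not.

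**Conclusion.** The concern holds as a risk of treatment-dependent censoring in secondary PFS and DOR beyond about 12 months. Under 11.3.3 the bias is probably upward if stopping for toxicity, illness or non-compliance carries a higher progression risk. Its size is roughly 1 to 4 points at 36 months for assumed ratios of 1.5 to 3 before late deaths, and nil or reversed at ratios of 1 or below. Late deaths can offset part of it. If last follow-up in 13.3 includes survival contact, PFS is inflated by about 1 to 9 points at 36 months and DOR is inflated too, whatever the patients' risk.

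A reader might infer that the patients cut off are a higher-risk group and that PFS and DOR are therefore overstated. The documents do not support that as fact: they give no off-treatment hazard and provide favourable routes off treatment. Nor does 11.3.3 govern DOR; only 13.3 does.

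The cap does not shorten follow-up for the 12-month CR endpoint, and 12-month PFS is essentially untouched. One inconsistency bears on the sign. Section 5.5 read literally, and footnote 6 to the correlative sample schedule (Table 10 in section 10), apply a one-year limit without exempting MRD-negative stoppers, contrary to section 5.6. These passages must be reconciled.

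**What to change.** 1. In 5.5, 5.6 and the Survival Status column of Table 9: at each survival contact for patients off treatment without progression, record from local records any progression (date and basis) and the start of the next CLL or Richter's therapy.
2. Count those progression dates as PFS and DOR events.
3. State one censoring rule across 11.3.3 and 13.3. It should define last follow-up and say how new therapy and late deaths are handled for each endpoint.
4. Report a sensitivity analysis restricted to protocol-scheduled, centrally read assessments.

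The cost is a few extra fields at contacts that already take place, for a subset of patients, with no added scans or visits and no change to treatment. The downside is that later progression dates rest on unscheduled local assessment, whereas section 11.3.4 has study scans read centrally; the sensitivity analysis shows how much that matters. It is a cheap improvement, best made before patients pass into survival-only follow-up, since these dates may be hard to recover afterwards.
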